Title	BETTER CARE – HF: Building Electronic Tools To Enhance and Reinforce Cardiovascular Recommendations – Heart Failure
Short Title	BETTER CARE – HF: Building Electronic Tools To Enhance and Reinforce Cardiovascular Recommendations – Heart Failure
Brief Summary	This study will test two types of electronic health record (EHR)-based alerts to improve guideline-adherent care for patients with heart failure and reduced ejection fraction (HFrEF). Alerts will be triggered for patients with ejection fraction (EF) \leq 40% who are not on guideline-recommended medical therapy. The two types of alerts tested will be a Best Practice Alert (BPA) and an electronic message.
Objectives	To test two types of EHR-based alerts that promote appropriate medical therapy for patients with HFrEF.
Methodology	Prospective cohort study
Endpoints	Primary endpoint: medication prescribing patterns Secondary endpoint: hospitalization and mortality
Study Duration	Eighteen months
Participant Duration	Eighteen months
Population	Patients with EF \leq 40%
Study Sites	One single health system, NYULH, consists of approximately 60 outpatient cardiology practices.
Number of participants	Up to 2000 participants
Statistical Analysis	We will begin all analyses with descriptive summary statistics and graphical displays of all variables. Primary analyses will utilize McNemar's tests for medication prescriptions and patient outcomes of hospitalization and mortality. We will adjust for patient demographics and clinical characteristics, as well as provider-level characteristics, such as demographics, panel size, insurance mix, and sub-specialty training.

CONFIDENTIAL

This material is the property of the NYU School of Medicine and Langone Medical Center. Do not disclose or use except as authorized in writing by the study sponsor

Schematic of Study Design

CONFIDENTIAL

This material is the property of the NYU School of Medicine and Langone Health. Do not disclose or use except as authorized in writing by the study sponsor

1 Introduction, Background Information and Scientific Rationale

1.1 Background Information and Relevant Literature

For patients with heart failure and reduced ejection fraction (HFrEF), the cornerstone of evidence-based care includes several medications that have been found to significantly reduce morbidity and mortality, which include: 1) mineralocorticoid antagonists (MRA), 2) angiotensin converting enzyme inhibitors, angiotensin receptor blockers, angiotensin receptor neprilysin inhibitors (ACE-I/ARB/ARNI), and 3) beta-blockers (BB). Current guidelines give these medications a class I recommendation,¹ and recently published performance measures² also strongly recommend these agents. However, despite their well-accepted benefits, several prior studies have revealed significant gaps in medical therapy for HFrEF patients.³⁻⁵ Using number-needed-to-treat estimates based on data from randomized trials, these gaps in medical therapy account for an estimated 68,000 deaths per year nationwide, with the largest proportion being from lack of appropriate MRA therapy.⁶

In prior studies, successful interventions for improvement have often included multidisciplinary approaches with nurses, pharmacists, or other trained individuals.⁷⁻⁹ However, the need for dedicated staff can be costly, and electronic health record (EHR)-based interventions could be a potential cost-effective solution. Prior studies assessing the efficacy of EHR-based interventions to improve medical therapy for HFrEF have mainly been conducted in the inpatient setting.¹⁰⁻¹² Inpatient algorithms may be limited as they reflect one instance in time. Additionally, acute hospitalization may restrict the ability to add multiple agents due to renal dysfunction or hypotension. Therefore, we propose the development of an outpatient EHR-based system to target patients with HFrEF who are not on the appropriate therapy.

Outpatient provider-facing EHR-based interventions could include best practice alerts (BPA) or electronic messages. While limited data exist for both types of interventions, some studies have observed significant improvements in health outcomes.¹³⁻¹⁵ Potential adverse effects have also been described, such as increased alert frequency with BPAs¹⁴ and physician burnout with electronic messages.¹⁶ Given the potential for benefit and/or harm, it is imperative to study such interventions with rigor. Currently, no study directly compares different types of EHR-based alerts.

In this study, we aim to test a BPA and an electronic message for HFrEF patients who are not on guideline-recommended therapy. This work is significant because it aims to reduce gaps in medical therapy for HFrEF patients, which we hope will reduce mortality, decrease hospitalizations, and improve symptoms.

We will not be directly recruiting or enrolling patients. However, we will be monitoring patients for clinical outcomes using EHR data and are requesting a waiver of authorization and consent.

We will also conduct a survey to assess provider acceptability and perceived usefulness and ease of use of the BPA and electronic messages. This survey will be sent to the cardiologists at NYULH who received the BPA and electronic messages.

1.2 Rationale

This study aims to evaluate EHR-based alerts to improve adherence to guideline-recommended medical therapy among patients with HFrEF.

Understanding provider feedback on the BPA and electronic messages is necessary to understanding why these EHR tools may or may not work to improve care. For example, the BPA may be more effective at improving prescribing, and the surveys could help us understand if this was because cardiologists thought that they were easier to use. Moreover, there may be drawbacks, such as increased time needed during visits due to the BPAs or electronic messages. The only way to obtain this type of information is from the cardiologists at NYULH who received the BPAs and electronic messages, as they are the only ones who can comment on the acceptability, usefulness, and ease of use of the EHR tools.

CONFIDENTIAL

This material is the property of the NYU School of Medicine and Langone Health. Do not disclose or use except as authorized in writing by the study sponsor

1.3 Potential Risks & Benefits

1.3.1 Known Potential Risks

The risk is not greater than minimal risk (i.e., risk encountered in daily life or in the course of usual clinical practice). Individual case determinations of potential safety gaps will never be released to supervisors of any clinicians whose charts are being reviewed.

The principal risk of the study, as for any medical record review, is inadvertent release of confidential patient information. We will avoid such inadvertent disclosure by storing all identifiable information on a secure server and restricting access to the data to authorized study personnel.

For provider surveys, we expect the level of risk due to this study to be minimal. Potential risks to providers may include the following issues listed.

- **Coercion/Undue Influence:** The study will include NYULH employees. Participants may feel coerced or under pressure to participate in the survey or provide positive remarks about their work activities. Staff will be informed that participation is solely voluntary and has no bearing on their employment status or salary. Additionally, employees will be informed that their decision to participate in the research study may not affect (favorably or unfavorably) performance evaluations, career advancement, or other employment-related decisions made by peers or supervisors.
- **Discomfort:** Participants may feel uncomfortable answering some of the study questions. They will be informed that they can refuse to answer any questions they wish. The information that we are retrieving is not sensitive in nature and we do not expect it to be of concern to the participant.

1.3.2 Known Potential Benefits

There may be benefit to individual patients for whom alerts may be triggered in this pilot study if their care is improved to comport with guidelines. The research will contribute critically to our knowledge of EHR-based alerts.

For the provider surveys, the information gained will put the effectiveness results into context (for example, help explain why one type worked better than another). Additionally, from an institutional quality improvement perspective, this will allow us to inform plans for next steps. The information gained from these surveys may also be beneficial to the providers themselves, as the feedback from this could impact next steps for the institution and future workflow within the EHR.

2 Objectives and Purpose

2.1 Primary Objective

The primary objective of the study is to evaluate EHR-based alerts to promote appropriate medical therapy for patients with HFREF.

3 Study Design and Endpoints

3.1 Description of Study Design

NYU Langone Health has ambulatory care sites in the five boroughs of New York City (NYC) as well as in suburbs of New York and New Jersey. All have the NYU Epic EHR.

3.2 Intervention

The two types of EHR-based alerts include: 1) BPA and 2) electronic message.

CONFIDENTIAL

This material is the property of the NYU School of Medicine and Langone Health. Do not disclose or use except as authorized in writing by the study sponsor

Best Practice Alert (BPA) – BPAs are alerts that appear at the time of the visit, allowing for real-time intervention while the provider is with a patient, but also potentially interrupting provider workflow. The BPA appears at the beginning of a visit/encounter and includes 1) a tailored advisory, 2) educational link to guidelines, 3) medication information, 4) vital sign and pertinent lab results, and 5) options for next steps (i.e. ordering medication, providing reasons for not prescribing).

Electronic Message – Unlike the BPA, the electronic message is not necessarily seen at the time of the visit, and is more likely to be seen between visits. The electronic message is similar to the BPA in terms of information provided, but can include information on multiple patients in the same message, and overall prescribing metrics.

3.3 Study Endpoints

Outcomes measured at the prescription encounter level include whether there is a prescription for BB, ACE-I/ARB/ARNI, and/or MRA. Secondary patient outcomes include hospitalization, hospitalization for HF, and mortality.

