4.2 Inclusion Criteria

- Patient with an encounter visit at NYULH cardiology practice during the study period
- Patient with EF \leq 40% on most recent echocardiogram
- Patient ages 18-100

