4.3 Exclusion Criteria

- Pregnancy
- Ventricular assist device
- In order to give providers time to add and up-titrate medications, we will exclude patients who had a newly reduced EF in the last 3 months.
- Medication-specific exclusion for MRA: most recent systolic blood pressure less than 105 mm Hg, most recent potassium < 5.1, any potassium > 5.5, most recent glomerular filtration rate < 30 (using MDRD equation), or a documented MRA allergy.

CONFIDENTIAL

This material is the property of the NYU School of Medicine and Langone Health. Do not disclose or use except as authorized in writing by the study sponsor

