5.3 Provider Survey Recruitment

For the provider survey, we will recruit cardiologists who received the BPA or electronic message through emails (see attachment). They will be made aware that completing the survey is completely anonymous and will in no way impact their employment. The recruitment emails will be sent via listservs of cardiologist who received the BPAs and electronic messages. These listservs are specific for those cardiologists who received BPAs or electronic messages and the survey does not require cardiologists to self-select whether they received a BPA or a message. Only cardiologists who received a BPA or electronic message will be contacted. We will send an initial recruitment email and a subsequent follow up email.

The consent form will be attached to the email. It will also be available via link within the first question in Qaltrix. The first question in Qaltrix asks the provider to review the consent document and requires the provider to click a button stating that they are consenting to participate before being shown the remaining survey questions. If the provider does not click this button, they will not be able to move forward or complete the survey.

6 Study Schedule

Participants will be included in this study by virtue of meeting eligibility criteria and having a patient encounter during the study period. There are no study-specific visits. Any patient meeting criteria who has one or more patient encounters during the study period will be included. Therefore, no study-specific visits are relevant for this study, so there is no schedule of visits.

CONFIDENTIAL

This material is the property of the NYU School of Medicine and Langone Health. Do not disclose or use except as authorized in writing by the study sponsor

7 Study Procedures / Evaluations

There are no study-specific procedures that patients will undergo. They will receive care as usual by their outpatient providers. The EHR algorithm developed by the study team identifies eligible patients with EF \leq 40% on most recent echocardiogram, and exclusion criteria listed above. The EHR algorithm will also capture information on demographics, diagnoses in the patient's problem list, prescription history, allergies, EF, and relevant lab results.

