9.2 Sample Size Determination

In order to have 80% power to detect a 10% improvement in prescribing for each intervention arm vs. control, we will require a total of at least 1503 patients (501 per arm). Based on prior data, we estimate that alerts will trigger for a sample between 1500-2000 patients, but are unable to accurately control the specific number of patients due to fluctuating clinical volume at practices.

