9.3 Statistical Methods

We will begin all analyses with descriptive summary statistics and graphical displays of all variables. Primary analyses will utilize McNemar's tests for medication prescriptions and patient outcomes of hospitalization and mortality. We will adjust for patient demographics and clinical characteristics, as well as provider-level characteristics, such as demographics, panel size, insurance mix, and sub-specialty training.

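### Prescribing is scored per encounter and the sample size counts patients, with no index encounter, window, combining rule, McNemar pair or limit to the missing drug class

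*Combined protocol and SAP*

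**What the plan says.** The prescribing outcome is defined only in Section 3.3: "Outcomes measured at the prescription encounter level include whether there is a prescription for BB, ACE-I/ARB/ARNI, and/or MRA". The Protocol Summary labels the primary endpoint as prescribing patterns and adds no definition.

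Four other places bear on it.

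- **Encounters.** Section 6: "Any patient meeting criteria who has one or more patient encounters during the study period will be included". Section 4.2 likewise requires only this: "Patient with an encounter visit at NYULH cardiology practice during the study period".
- **Sample size.** Section 9.2 counts patients: "we will require a total of at least 1503 patients (501 per arm". It describes them by the trigger: "we estimate that alerts will trigger for a sample between 1500-2000 patients". The comparison is each alert arm against control.
- **Trigger.** The Brief Summary says alerts fire for patients with reduced EF "who are not on guideline-recommended medical therapy". Neither Section 4.2 nor Section 3.3 carries that condition.
- **Analysis.** Section 9.3 makes the primary analyses McNemar's "tests for medication prescriptions and patient outcomes of hospitalization and mortality", then promises adjustment for patient and provider characteristics.

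No section names an index encounter, a prescribing window, a rule for combining encounters, or the pair that McNemar's test would compare. The 18 months in Sections 5.1 and 7 is a monitoring period and is not tied to an encounter or an alert. The design schematic was not available in the text reviewed, and nothing here rests on it.

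**The concern.** Two separate questions are left open until the data are in hand.

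**Unit.** A patient seen several times contributes several outcomes under Section 3.3 but one unit under Section 9.2. Encounters of one patient resemble each other. A between-arm test that treats them as independent uses a standard error that is too small and rejects a true null too often.

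**Which prescription counts.** A patient is alerted because something is missing, but Section 3.3 does not confine scoring to what was missing. Under an any-class reading, a patient alerted for a missing MRA could score yes through a beta-blocker already taken. Under a class-by-class reading that cannot happen for MRA. The same patient would still score yes on beta-blocker in every arm if everyone is in that denominator. Either way, patients who cannot change would pull the arms together.

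First, last, any or every encounter, and new starts or existing treatment, can each give a different primary result from the same records.

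**Working it through.** **The plan's own figure.** 3 × 501 = 1503 agrees. The 501 itself cannot be uniquely reproduced, because Section 9.2 gives no alpha, sidedness or control rate and does not say whether the 10% is absolute or relative.

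- Absolute 10 points, two-sided alpha 0.05, 80% power, unpaired: the largest requirement at any control rate is 392 per arm (412 with continuity correction).
- Alpha 0.05/3: control rates near 0.35 or 0.55 give 501.
- Relative 10% at alpha 0.05: the requirement falls from 558 to 466 as the control rate goes from 0.72 to 0.75, so it passes 501 on the way.
- McNemar's test with 64% discordant pairs: 500 pairs.

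Several input sets fit, so 501 is neither confirmed nor shown wrong.

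**Encounters treated as independent, between arms.** The documents give neither the number of encounters per patient (m) nor their correlation (ρ); both are assumed. Variance inflation is V = 1 + (m−1)ρ. True error at nominal 5% is 2[1 − Φ(1.96/√V)].

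| m | ρ | V | 1.96/√V | Error |
|---|---|---|---|---|
| 2 | 0.3 | 1.3 | 1.719 | 8.6% |
| 3 | 0.6 | 2.2 | 1.321 | 18.6% |
| 4 | 0.8 | 3.4 | 1.063 | 28.8% |

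Simulating McNemar's test under the null (501 patient pairs matched across arms, m encounter pairs each, beta-binomial outcomes with mean 0.3) gives 8.5, 18.3 and 28.6%, against 4.9% with one encounter per patient.

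**Same-patient before/after pairs.** With the same set-up but each pair taken within one patient whose propensity does not change, the error is 5.2, 4.6 and 4.8%, so there is no inflation. It would return if patients' changes over time varied.

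**Drugs already taken.** Let f be the share already scoring yes at baseline, and p0 and p1 the new-start rates in the rest. The arms show f + (1−f)p0 and f + (1−f)p1, a difference of (1−f)(p1 − p0). The documents do not give f.

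| f | 10 points among off-class patients shows overall as 10(1−f) | Off-class rise needed for 10 points overall, 10/(1−f) | Off-class patients per arm, 501(1−f) |
|---|---|---|---|
| 20% | 8 | 12.5 | 401 |
| 30% | 7 | 14.3 | 351 |
| 50% | 5 | 20 | 250 |
| 80% | 2 | 50 | 100 |

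As a scenario, take new starts of 20% vs 30%, 501 per arm and two-sided alpha 0.05. Power scoring everyone is 73, 60, 37 and 14% down the rows. Power in off-class patients only is 91, 87, 74 and 37%. At f = 0 this scenario has 96% power, not the plan's 80%, so only the ordering is informative. Clinic clustering is ignored throughout.

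**The case against.** The strongest reply has four parts.

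1. **The error rates belong to one pairing.** Section 9.3 names no pair, and no section describes matching patients across arms. Before/after pairs are an available reading and gave about 5%. This stands. A reader might infer that the trial will run at 9 to 29% error, but the documents do not support that. They give no m or ρ and do not say that encounters will be treated as independent. What remains is that Section 9.2 frames the comparison as each arm against control, and Section 9.3 states no allowance for repeated encounters. Covariate adjustment is not such an allowance, and McNemar's test cannot itself carry it.

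2. **Counting treated patients may be intended.** Section 9.1 speaks of adherence, and Section 9.2 does not confine its 10% to untreated patients. At an encounter, a prescription may also mean an order placed then, so a drug already taken would score only if re-ordered. This stands too. A reader might infer that the endpoint is wrong or the study underpowered. If the 10% refers to the outcome as written, power is not reduced, and the consequence is instead the larger rise required among off-class patients.

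3. **The alerted population is stated elsewhere.** It is, in the Brief Summary and Sections 1.1, 7 and 9.2. That fixes who is alerted but not which class scores.

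4. **Orders between visits.** Section 3.2 expects messages to be read mostly between visits, and Section 3.3 does not say whether orders placed then count. That is a point to clarify, not an error.

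**Conclusion.** The definitional gap holds. The outcome is per encounter, the sample size is in patients, and the index encounter, window, combining rule and McNemar pair are all missing. This should be settled before analysis, because it determines the primary result.

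The size is conditional. A between-arm test on encounters treated as independent would have about 9, 19 or 29% error under the three assumed settings. Before/after pairs with unchanged propensity would have none of that inflation. Dilution to 10(1−f) points applies only if drugs already taken count as success and the 10 points are meant among off-class patients. If overall adherence is the target, the scoring is by design and the requirement becomes 10/(1−f) points among off-class patients. A reader might also infer that 501 per arm is wrong; the check above does not show that.

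**What to change.** **Section 3.3.** Define one binary primary outcome per patient, to match Section 9.2: a new order, at a visit or between visits, within a fixed stated window from the first qualifying encounter, of a class the patient was off at baseline. Set the baseline date before any alert or message could act, and identify it the same way in all arms, including control. Otherwise patients who responded to an early message could be dropped as already treated. Analyse each class in patients off it at that baseline, name the primary class or composite, and keep overall adherence as a secondary outcome.

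**Section 9.3.** Replace the McNemar comparison, or define it so that it is a between-arm test with the patient as the unit. The edit to Section 3.3 alone does not supply a pair.

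**Section 4.3.** Class-specific limits exist for one class only ("Medication-specific exclusion for MRA"). Its two potassium limits, taken together as written, leave only a most recent value between 5.1 and 5.5. They must be reconciled before they define a denominator.

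**Cost.** The change is mainly wording, since Section 7 already has the algorithm capture prescription history. Denominators shrink for widely used classes (401, 351, 250 or 100 per arm at f = 20, 30, 50 or 80%, before any MRA exclusions). The primary estimand becomes new starts rather than overall adherence. If the sponsor prefers adherence as primary, one outcome per patient and the change to Section 9.3 still apply.

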For patients meeting the eligibility criteria, a message in the EHR will automatically be sent to the provider. The provider will receive either a Best Practice Alert (BPA) or electronic message indicating that their heart failure patient is not on guideline-recommended therapy. The message will offer guidance for physician decision-making regarding HFrEF care. The study team presented the proposed project to the NYULH MCIT Project Portfolio Review Committee on February 11, 2021 and was approved to work with MCIT to build the electronic messages. Providers will be notified through the Weekly Epic Update and in presentations to medical directors that they may see the alert prior to the start of the study.

Patients' clinical outcomes will be monitored through EHR data collection for 18 months. Data collection will include elements of protected health information including patient name, medical record number, address zip code, and service dates. These will be necessary for data linkages and in order to track patients for receipt of intervention and clinical outcomes. All PHI data will be kept on a secure NYULH server and destroyed at the earliest possible point. Data on the patient's medication prescription, hospitalization, hospitalization for HF, and mortality will be recorded as study outcomes. The study team members will not collect this information directly; data will be collected in NYULH's EHR system, EPIC, and an EPIC Reporting analyst from DataCore will extract the relevant parameters from the EHR into a report.

Data points that will be collected for research purposes
Medication prescription
Hospitalization
Hospitalization for HF
Mortality
Name
Medical record number
Address zip code
Service dates

Provider survey data will be anonymously collected via Qualtrix. No identifiable information, PII, or health information will be collected. The URLs for the survey are below:

BPA version = https://nyumc.yul1.qualtrics.com/jfe/preview/previewId/f42fb1cb-b997-4fb8-8f60-9e311e6b6320/SV_7P3UhfVSH6KgpuK?Q_CHL=preview&Q_SurveyVersionID=current

IBM version = https://nyumc.yul1.qualtrics.com/jfe/preview/previewId/c97ab951-3feb-478a-8af8-a53e9abbe02d/SV_7PQoQunPLM8I8ZU?Q_CHL=preview&Q_SurveyVersionID=current

8 Safety and Adverse Events

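### The alerts aim to raise prescribing of three drug classes including MRA, yet no potassium or renal safety outcome is planned, although the protocol uses both to limit MRA alerts

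*Combined protocol and SAP*

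**What the plan says.** - **Outcomes.** Section 3.3 lists prescribing outcomes that "include whether there is a prescription for BB, ACE-I/ARB/ARNI, and/or MRA", and then: "Secondary patient outcomes include hospitalization, hospitalization for HF, and mortality". Section 7 repeats the set: "Data on the patient's medication prescription, hospitalization, hospitalization for HF, and mortality will be recorded as study outcomes". The table of research data points that follows in Section 7 has no laboratory value.
- **Labs as a limit on the intervention.** The MRA-specific exclusion in Section 4.3 includes "any potassium > 5.5, most recent glomerular filtration rate < 30 (using MDRD equation"), alongside a limit on the most recent potassium, a blood pressure limit and MRA allergy.
- **Labs in the system.** Section 7 says the algorithm captures "prescription history, allergies, EF, and relevant lab results". Section 3.2 says the BPA shows "vital sign and pertinent lab results". Neither says whether results after the alert are extracted.
- **Drug tolerance.** Section 1.1 notes that kidney dysfunction and low blood pressure can limit how many agents are added during an acute admission.
- **Adverse events.** Section 8.1 counts an abnormal test as an adverse event under listed conditions. Section 10 says there are no study case report forms. No section describes systematic collection of such events or a comparison by arm.

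**The concern.** The intervention works only by getting more patients onto beta-blockers, ACE-I/ARB/ARNI or MRA. The protocol treats potassium and GFR as reasons not to prompt for an MRA, so it recognises them as the laboratory limits on that drug. It reads them before the alert but plans no look at them afterwards.

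If prescribing rises, the trial will report success on a process measure. It will have no by-arm information on the laboratory harm most directly tied to part of that rise. Potassium or renal changes managed in clinic would leave no trace in the listed outcomes. Those leading to admission would be mixed with all other admissions and could be offset by benefit from the added therapy.

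**Working it through.** **1. Outcomes against limits.**

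| Item | Used to restrict the MRA alert (4.3) | Listed as outcome (3.3, 7) |
|---|---|---|
| Potassium | yes | no |
| GFR | yes | no |
| Hospitalization, HF hospitalization, mortality | no | yes |

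**2. The plan's own figure.** Section 9.2 gives 501 per arm (1503 in total) for 80% power to detect a 10% improvement. It states no baseline rate, alpha or sidedness, nor whether 10% is absolute or relative, so 501 cannot be derived from the stated inputs. It is attainable under unstated choices (for example, two-sided alpha 0.0167 with a 35% baseline and a 10-point gain gives 501). Nothing here depends on that; 501 is used only as the arm size.

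**3. Precision of an added laboratory outcome.** Control rates p are assumed, because the documents give none. Half-width = 1.96 × √(2p(1−p)/501):
- p = 2%: 1.96 × √(0.0392/501) = 1.7 points
- p = 5%: 1.96 × √(0.0950/501) = 2.7 points
- p = 10%: 1.96 × √(0.1800/501) = 3.7 points

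These take all 501 as tested, eligible and independent. If only half are tested and eligible, each is multiplied by √2, giving 2.5, 3.8 and 5.3. Clustering widens them further.

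**4. What difference to expect.** Assume a 10-point rise in MRA prescribing. Section 9.2 names no drug class, so this is an assumption. Then 0.10 × 501 ≈ 50 more patients are treated per arm. If each has an assumed excess risk of 10% to 20%, the arm difference is 0.10 × 10% to 0.10 × 20% = 1 to 2 points.

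For a 2-point difference at a 2% control rate, the half-width is 1.96 × √((0.04 × 0.96 + 0.02 × 0.98)/501) = 2.1 points. The interval is −0.1 to 4.1 and includes zero. The same formula gives −0.9 to 4.9 at 5% and −1.9 to 5.9 at 10%.

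**5. What could be shown.** The observed difference must reach about 2.1, 3.1 or 4.0 points at 2%, 5% or 10% before the interval clears zero. Divided by 0.10, that is an excess risk of about 21%, 31% or 40% per added patient. For 80% power at two-sided 0.05, the true difference must be about 3.4, 4.6 or 6.0 points. Power for a true difference of 1 to 2 points is about 7% to 46%.

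**6. Potassium limits in Section 4.3.** Excluding a most recent value < 5.1 leaves values of 5.1 or more. Excluding any value > 5.5 leaves values of 5.5 or less. Together only most recent values from 5.1 to 5.5 remain eligible for an MRA alert. The two limits run in opposite directions.

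**The case against.** The case against is that this is a minimal-risk pilot of prompts for drugs with a class I recommendation, that prescribers keep their autonomy, and that the added table would have little power. Several parts of this stand.

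- A reader might infer that drug harm would be wholly invisible. The documents do not support that. Harm severe enough to cause admission or death enters all-cause hospitalization and mortality over 18 months, and Section 8.1.1 requires reporting of unanticipated related problems and of new information on risk. What is missing is identification, attribution and comparison by arm.
- A reader might take the sentence in Section 1.1, "Given the potential for benefit and/or harm, it is imperative to study such interventions with rigor", as an acknowledgement of drug toxicity. The harms named just before it are alert frequency and physician burnout, and the provider survey in Section 3.4 addresses alert fatigue. The support for this point is Section 4.3 and the remark on renal dysfunction and hypotension.
- A reader might infer that 501 per arm could detect or rule out any clear excess. Steps 4 and 5 show otherwise.
- A reader might infer that post-alert labs are already collected and thrown away. Section 7 describes capture by the algorithm that identifies eligible patients and gives no timing. Its data table is also not a full inventory: it omits the demographics and clinical characteristics that Section 9.3 adjusts for.
- A reader might infer that the consent waiver obliges the study to make this comparison. Section 11.3 sets no such condition.
- A bare count of GFR < 30 would mislead. The laboratory limits apply only to the MRA alert, so patients already beyond them may be in the study for the other two classes.

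None of this supplies the missing outcome. Low power argues for estimation without a test, not for leaving the result out.

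**Conclusion.** The gap is real but limited. Sections 3.3 and 7 name no laboratory outcome, while Section 4.3 makes potassium and GFR limits on the MRA alert. Harm without admission would be missed; harm with admission could not be attributed. The prescribing comparison is unaffected, but any statement on benefit against risk would be incomplete.

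This is a cheap improvement with modest yield: half-widths of about 1.7 to 3.7 points under assumed control rates of 2% to 10%, at best. It could show a large excess, but would probably not settle a 1- to 2-point one.

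The conflicting potassium limits are a separate eligibility problem. They do not prove that a safety outcome is missing, but they determine who is in the proposed analysis population.

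**What to change.** 1. Add to Section 3.3 and to the Section 7 data list a descriptive safety outcome from routine EHR labs, using the protocol's own values: any potassium > 5.5, and GFR newly < 30, within a stated window after the index encounter.
2. Analyse it in patients eligible for the MRA alert at index, identified by the same algorithm in all arms including control. Define the index encounter identically in each arm, since the electronic message is not tied to a visit. Exclude or account for patients already beyond a limit at baseline, and state how those without a baseline result are handled.
3. Report by arm the proportion tested, with a rule for untested patients, and the difference with a cluster-adjusted confidence interval. Do not attach a significance test.
4. Confirm with the reporting analyst that results after the alert are in the extract.
5. Separately, reconcile the potassium limits in Section 4.3 and check how the alert logic was built. Which limit is intended is for the sponsor to state.

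**Cost.** Two laboratory fields, their dates and one table, with no extra visits or tests. If post-alert results are not yet extracted, the report specification must be extended. The main drawback is detection bias: if alert arms are tested more often, more abnormal values will be found, which is why the testing proportion must stand beside the result.
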